# C. Background and Significance

Bipolar disorder (BD) is a serious mental health condition marked by significant mood instability, which impairs emotion regulation and leads to functional difficulties [1]. Unlike unipolar depression, BD involves rapid and intense mood fluctuations, including difficulty sustaining negative emotions [2]. These patterns suggest that BD is defined more by dynamic instability than by persistent mood states.

Neuroimaging studies have revealed abnormalities in emotion-related brain circuits, including decreased activity in regulatory regions like the anterior cingulate cortex (ACC) and prefrontal cortex (PFC), and increased activity in emotion response regions (e.g., amygdala) [3, 4]. BD is also associated with altered connectivity in the default mode and frontoparietal networks [5]. Dynamic functional connectivity studies show increased variability in brain states, but these methods are limited by low temporal resolution and interpretability [6, 7].

To address these gaps, this study will decode emotional states from whole-brain fMRI patterns using machine learning [8, 9] and quantify emotional dynamics using complexity science and network control theory [10, 11]. We will also evaluate how positive emotion amplification strategies influence emotional stability, informed by evidence from Amplification of Positivity (AMP) psychotherapy and neurofeedback [12, 13]. This approach offers a novel framework for understanding mood instability in BD and identifying targets for personalized, adaptive interventions.

## D. Criteria for Participant Selection

#### Target Recruitment:

- 32 individuals with BD (BD-I or BD-II, currently in a depressive or mixed state)
- 32 healthy control participants

#### Inclusion and Exclusion

#### **Inclusion Criteria**

- 1. Age 18 to 65 years
- 2. Male or female
- 3. BMI between 18.5 and 38.0 kg/m^2 at Screening
- 4. Capable of understanding and complying with study requirements
- 5. Fluent in English
- 6. Able to provide informed consent

## **BD Group:**

- 7. Meet the DSM-5 diagnostic criteria for BD-I or BD-II who are currently depressed or mixed state defined by the Mini-International Neuropsychiatric Interview (MINI) [14]
- 8. Moderate or greater depressive symptom severity (MADRS ≥ 15 or PHQ-9 ≥ 10)

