## **Summary of Changes from Previous Version:**

Version Information	Summary of Revisions Made	Rationale
V2 10/13/2025	
 
Section D, Inclusion Criteria:** Added PHQ-9 to inclusion criterion #8.
 
Section D, Exclusion Criteria (#4):** Revised to read: "Drug or alcohol intoxication (based on a positive UTOX or breathalyzer test at screening or study session), or reported alcohol/drug withdrawal. Last cannabis use must be >48 hours prior to the study session."
 
	
 
To accommodate the practical screening procedures and maintain consistency with a previous project. PHQ-9 is included in the NeuroMAP Core data collection, which all participants will be recruited through (Section E). A PHQ-9 score ≥10 is considered equivalent to a MADRS score ≥15 in depressive severity.
 
To make the exclusion condition more practical and operationally.
 

- 3. Section D, Exclusion Criteria (#9):\*\*
  Removed the criterion: "Prescription of a medication outside of the accepted range, as determined by the best clinical practices and current research."
- 4. Section F, Table 1:\*\* Moved the clinicianadministered depression and mania assessments (MADRS and YMRS) to the day of scanning.
- 5. Section F, Figure 1:\*\* Removed the second resting-state scan from the MRI session.
- 6. Section F, Think and Regulate Affective States Task (TReAT):\*\* Increased the number of attention trials from four 3-second trials to six 2-second trials.
- 7. Section J, Psychiatric or Behavioral Risk:\*\*
  Added "Current DSM-5 diagnosis of" before
  "moderate-to-severe substance use disorder."

- 3. This exclusion is beyond the scope of the study's monitoring and cannot be reliably assessed within the study's procedures.
- 4. To ensure that symptom ratings reflect participants' clinical status at the time of imaging, as symptoms may change between the preparation visit and the scan day.
- 5. To ensure the total MRI session is completed in under two hours and to prioritize scans most relevant to the study aims. The second resting-state scan was deemed least essential.
- 6. To increase task demand and more effectively clear participants' thought states between affective task periods.
- 7. To clarify and specify the diagnostic basis for determining exclusion due to substance use disorder.

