#### **Exclusion Criteria**

- 1. No telephone or easy access to telephone
- 2. Significant medical problems as identified by the medical screening questionnaire: e.g. a history of unstable liver or renal insufficiency; glaucoma; significant and unstable cardiac, vascular, pulmonary, gastrointestinal, endocrine, neurologic, hematologic, rheumatologic, or metabolic disturbance; or any other condition that, in the opinion of the investigator, would make participation not be in the best interest (e.g., compromise the well-being) of the participant or that could prevent, limit, or confound the protocol-specified assessments
- 3. A positive test for drugs of abuse, including alcohol (breath test), cocaine, opiates, amphetamines, methamphetamines, phencyclidine, benzodiazepines, barbiturates, methadone, and oxycodone
- 4. Drug or alcohol intoxication (based on positive UTOX or breathalyzer test at screening or study session) or reported alcohol/drug withdrawal, last cannabis use must be >48 hours prior to study session.
- 5. Current DSM-5 diagnosis of a psychosis spectrum disorder or moderate to severe substance use disorder
- 6. Moderate to severe traumatic brain injury or other neurocognitive disorder with evidence of neurological deficits, neurological disorders, or severe or unstable medical conditions that might be compromised by participation in the study (to be determined by primary care provider)
- 7. Current significant suicidal ideation or suicide attempt within the past 3 months.

- 8. Change in the dose or prescription of a medication within the 6 weeks before enrolling in the study that could affect brain functioning, e.g., anxiolytics, antipsychotics, antidepressants, or mood stabilizers
- 9. Taking drugs that affect the fMRI hemodynamic response (e.g., methylphenidate, acetazolamide, excessive caffeine intake > 1000 mg/day)
- 10. MRI contraindications as documented on the MR Environment Screening
- 11. Unwillingness or inability to complete any of the major aspects of the study protocol, including magnetic resonance imaging (i.e., due to claustrophobia), or behavioral assessment. However, failing to complete some individual aspects of these assessment sessions will be acceptable (i.e., being unwilling to answer individual items on some questionnaires or being unwilling to complete a behavioral task)
- 12. Non-correctable vision or hearing problems

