#### E. Recruitment and Retention Plans

## Recruitment Strategy

Participants will be recruited through:

• The NeuroMAP Recruitment and Assessment Core at LIBR (WCG IRB# 20231660)

During NeuroMAP Core study procedures, initial eligibility screening will occur via phone. Individuals who meet preliminary criteria will be invited for an in-person screening session, where they will undergo a structured psychiatric assessment using the MINI interview and standardized self-report measures. No identifying information will be collected prior to voluntary contact with LIBR research staff. Once NeuroMAP Core data collection is complete, study staff will screen subjects against the eligibility criteria listed above. Trained study staff will contact individuals who are determined to be initially eligible to confirm eligibility and interest in discussing the informed consent.

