## Session Timeline

The study sessions consist of two visits: one preparation session and one MRI scanning session. Table 1 describes the overall outline of this study and measures obtained at different points in time.

Table 1. Experimental procedure and Assessments

		Visit1		Visit 2		
Content	Procedures/Assessments		1-7 days after Visit 1			
			Before MRI	During MRI	After MRI	
Informed Consent		Χ				
Mania	Young Mania Rating Scale (YMRS)		X			
Depression	Montgomery–Åsberg Depression Rating Scale (MADRS)		X			
Trait Rumination	Ruminative Response Scale (RRS) [15]	Х				
State Rumination	Brief State Rumination Inventory (BSRI)	Х	X			
Hedonic	Temporal Experience of Pleasure Scale (TEPS)	Х				
Emotion Regulation	Emotion Regulation Questionnaire (ERQ)	Х				
Emotion Regulation	Difficulties in Emotion Regulation Scale (DERS)	Х				
Positive/	Positive and Negative Affect Schedule-	Х	X		X	
Negative Valence	X (PANAS-X)					
Depression	16-item Quick Inventory of Depressive Symptomatology (QIDS)	Х	X			
Social Functioning	Sheehan Disability Scale (SDS)	Х				
Trait-anxiety	State Trait Anxiety Inventory (STAI-T)	Х				
State-anxiety	State Trait Anxiety Inventory (STAI-S)		Х		Х	
Depression	PROMIS Depression	X				
Anxiety	PROMIS Anxiety	Х				
Hedonia	PROMIS General Self-Efficacy Scale	Х				
Anger	PROMIS Anger	X				

Hedonia	PROMIS Positive Affect and Wellbeing	Х			
Subjective cognitive abilities	PROMIS Applied Cognition-Abilities	Х			
Subjective cognitive concerns	PROMIS Applied Cognition-General Concerns	X			
Physical function	PROMIS Fatigue	X			
Sleep	PROMIS Sleep Impairment and Disturbance	Х			
Thought collection wor	k sheet (study original)	X			
Emotion Intencity of events	Likert scale for positive or negative emotions	х	X		
MRI screening	MRI safety-screening questionnaire		Χ		
Alcohol and drug	Breathalyzer and urine drug screening test		X		
Pregnancy (only for female)	Urine-screening pregnancy test		Х		
Emotional State	Affective slider (emotional valence and arousal)			X	
Fatigue	Likert scale (study original)			Χ	
Comfort during the session	Feedback Questionnaire † (study original)				Х
Physiological measurement (Cardiogram, Respiration)				Χ	

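### Does inclusion criterion 8 break down because the MADRS is scheduled only on scan day?

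*Protocol*

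**What the plan says.** Section D (BD Group, item 8) sets the severity requirement as "Moderate or greater depressive symptom severity (MADRS ≥ 15 or PHQ-9 ≥ 10", on top of a current depressed or mixed state by the MINI (item 7). It gives no time point for either scale.

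Section E (Recruitment Strategy) gives the order of events. The in-person Core session comprises a "structured psychiatric assessment using the MINI interview and standardized self-report measures". Then: "Once NeuroMAP Core data collection is complete, study staff will screen subjects against the eligibility criteria listed above". Those who look eligible are contacted "to confirm eligibility and interest in discussing the informed consent".

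Section F has consent signed at Visit 1 and places Visit 2 one to seven days after Visit 1 is complete. In Table 1 the row "Montgomery–Åsberg Depression Rating Scale (MADRS" (abbreviation closing there) has a single mark, at Visit 2 before the MRI.

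The Summary of Changes agrees with the current Table 1. It reports moving the clinician-rated "depression and mania assessments (MADRS and YMRS) to the day of scanning", so that ratings describe the participant's state when imaged. It also explains why the PHQ-9 joined criterion 8: "PHQ-9 is included in the NeuroMAP Core data collection", all participants are recruited through the Core, and the two cutoffs are taken as equivalent in severity.

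**The concern.** A criterion with two arms should allow both to be applied at the step where it is judged. Here one arm uses a clinician rating that this protocol first obtains after eligibility has been confirmed, consent signed and Visit 1 completed. Two readings seem possible.

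- **(a)** Candidates with a Core PHQ-9 below 10 are screened out. Criterion 8 is then in practice a PHQ-9 criterion, and the published criterion shows a MADRS route that was never used.
- **(b)** Such candidates are consented, complete Visit 1 and are judged by the scan-day MADRS. Their eligibility is then unknown until late, and the withdrawal section does not list an unmet inclusion criterion among its reasons.

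If staff differed in their reading, the same person could be admitted by one and refused by another. The make-up of the bipolar sample and its description in a report would be at stake.

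**Working it through.** No figure in the protocol depends on this point, so the check is mainly a comparison of sections.

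**1. What is known at each step**

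| Step | Source | PHQ-9 | MADRS |
|---|---|---|---|
| Core session | Section E; Summary of Changes | available | not mentioned |
| Screening against criteria, confirming contact | Section E | available | not scheduled |
| Consent and Visit 1 | Section F, Table 1 | already known | not scheduled |
| Visit 2, before MRI | Table 1 | already known | first scheduled rating |

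The observation is correct: at the point of decision, the protocol provides for the PHQ-9 only.

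**2. Does the criterion still work?** The arms are joined by *or*, so one score is enough to admit. Every candidate has a Core PHQ-9, so every candidate can be judged at the Section E step. Nobody is left without a severity measure.

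**3. Which reading does the text favour?** Reading (a). Section E confirms eligibility before consent is discussed, and the Summary of Changes gives the scan-day MADRS a different role, state at imaging. No section says that a candidate below 10 on the PHQ-9 is consented and then judged on scan day.

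**4. What reading (b) would cost, from Table 2.** Visit 1 takes 2.5 hours and pays $50. The pre-MRI symptom evaluations add 1.0 hour and $20.

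- Time before the MADRS is known: 2.5 to 2.5 + 1.0 = 3.5 hours of 6.5; 3.5 / 6.5 = 54%.
- Payment: $50 to $50 + $20 = $70 of $190; 70 / 190 = 37%.

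These costs arise only under the reading that the text does not support.

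**5. Is a missing time point unusual here?** Exclusion 4 does name one, "based on positive UTOX or breathalyzer test at screening or study session", which might suggest that silence in criterion 8 is significant. But exclusion 3 (a positive drug or alcohol test) names none, although Table 1 schedules that test only at Visit 2. Exclusion 10 names none either, although the MR screening form is completed on scan day. Silence on timing is common in this list.

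**6. Does silence in the withdrawal section leave no rule?** That section also omits a positive drug test, a positive pregnancy test and a newly found MRI contraindication, all of which clearly bar scanning under other sections. The Section D criteria bind in their own right.

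**7. Sample size.** The target of 32 per group at d = 0.71 does not depend on which arm admits a person. With a two-sided 5% t-test (alpha is not stated; this is an assumption), power is 0.798, which reproduces the stated 80% under either reading.

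**The case for a change.** The strongest case for a change is that the current sections do not fit together, whatever earlier text said. Someone scoring below 10 on the PHQ-9 and at least 15 on the MADRS meets criterion 8 as written, yet the protocol offers no way to identify that person before enrolment. One or two sentences would remove the mismatch: name the score and time point that decide entry, and describe the scan-day MADRS as a measure of state at imaging.

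Most of this stands as description. The mismatch is real, and it probably arose because the MADRS was kept as an entry measure while its rating was moved to scan day. A sponsor amending the protocol for other reasons could well add the clarification.

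It does not carry further than that. The clarifying sentence would record what staff following Section E already do. Adding an earlier MADRS to rescue the unused arm would require an extra clinician rating that no stated aim needs. The number of people affected cannot be drawn from the documents: it depends on the correlation between the scales and on the share of candidates above each cutoff, and neither is given. The Core has its own protocol, which is not at hand, so a MADRS there cannot be ruled out, although the reason given for adding the PHQ-9 suggests there is none.

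**Conclusion.** The mismatch is a clerical one, and no change to the plan is needed. Criterion 8 can be applied to every candidate before consent through the PHQ-9, at a cutoff the sponsor regards as equivalent to the MADRS cutoff. The scan-day MADRS remains available to describe the sample at imaging. The effect is limited to candidates below 10 on the PHQ-9 who would have scored 15 or more on the MADRS. Their number is unknown, and leaving them out harms neither the validity of the bipolar sample nor its size. No effect on the comparison with healthy controls, on power or on safety is shown.

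This rests on two statements in the Summary of Changes: that all participants come through the Core with a PHQ-9, and that the two cutoffs are equivalent. It also rests on Section E being followed in the order written. A report of the trial should say which score admitted the participants.

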## **HC Group:**

9. No current or past psychiatric disorder (verified by MINI)

#### **Exclusion Criteria**

- 1. No telephone or easy access to telephone
- 2. Significant medical problems as identified by the medical screening questionnaire: e.g. a history of unstable liver or renal insufficiency; glaucoma; significant and unstable cardiac, vascular, pulmonary, gastrointestinal, endocrine, neurologic, hematologic, rheumatologic, or metabolic disturbance; or any other condition that, in the opinion of the investigator, would make participation not be in the best interest (e.g., compromise the well-being) of the participant or that could prevent, limit, or confound the protocol-specified assessments
- 3. A positive test for drugs of abuse, including alcohol (breath test), cocaine, opiates, amphetamines, methamphetamines, phencyclidine, benzodiazepines, barbiturates, methadone, and oxycodone
- 4. Drug or alcohol intoxication (based on positive UTOX or breathalyzer test at screening or study session) or reported alcohol/drug withdrawal, last cannabis use must be >48 hours prior to study session.
- 5. Current DSM-5 diagnosis of a psychosis spectrum disorder or moderate to severe substance use disorder
- 6. Moderate to severe traumatic brain injury or other neurocognitive disorder with evidence of neurological deficits, neurological disorders, or severe or unstable medical conditions that might be compromised by participation in the study (to be determined by primary care provider)
- 7. Current significant suicidal ideation or suicide attempt within the past 3 months.

- 8. Change in the dose or prescription of a medication within the 6 weeks before enrolling in the study that could affect brain functioning, e.g., anxiolytics, antipsychotics, antidepressants, or mood stabilizers
- 9. Taking drugs that affect the fMRI hemodynamic response (e.g., methylphenidate, acetazolamide, excessive caffeine intake > 1000 mg/day)
- 10. MRI contraindications as documented on the MR Environment Screening
- 11. Unwillingness or inability to complete any of the major aspects of the study protocol, including magnetic resonance imaging (i.e., due to claustrophobia), or behavioral assessment. However, failing to complete some individual aspects of these assessment sessions will be acceptable (i.e., being unwilling to answer individual items on some questionnaires or being unwilling to complete a behavioral task)
- 12. Non-correctable vision or hearing problems

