#### Participant/Representative Comprehension

During the written informed consent process, the participant's understanding of the study protocol will be assessed and documented by trained study staff. If a participant is unable to demonstrate adequate understanding of the protocol, they will not be enrolled in the study.

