## Self-Report Measures

After the informed consent document is signed during Visit 1, the study participants will be asked to complete a series of questionnaires either in-person using a LIBR iPad or computer, or remotely using a link sent to the participant's email. Data collected from these questionnaires will be used to characterize the study population and examine how individual differences relate to brain activation metrics.

Participants will be asked to complete several questionnaires related to mood, clinical symptoms, traits and personality characteristics, daily life functioning, and medical and mental health history. These self-report questionnaires are listed in Table 1. Self-report measures may be completed at home using a link from REDCap, as needed.

Participants will recall eight autobiographical events, each clearly associated with one of two thinking patterns: rumination (past negative events) or reminiscence (past positive events), which will be used in the MRI task. They will generate four events per category and write brief, keyword-based descriptions to assist with memory recall inside the MRI scanner. Details of each event will not be requested, allowing participants to provide personal events honestly.

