#### **MRI Scanning Visit**

Participants will be scheduled for Visit 2 one to seven days after Visit 1 is complete. The following instruments and scans will be conducted during the MR scanning visit.

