## **Participant Discontinuation and Withdrawal**

Participants will be informed that participation is completely voluntary and that they may withdraw from the study at any time. If a participant withdraws or is discontinued, the reason and the method used to determine the need for discontinuation will be documented. Participants will be withdrawn if they revoke consent or if the investigator determines that continued participation is not in their best interest. This may include newly emerging or worsening suicidal ideation. Participants may also be withdrawn if they do not comply with staff instructions or are unable to remain still in the MRI scanner and continue to exhibit frequent motion despite guidance, as excessive motion renders the MRI data unusable. In the event of a system failure that prevents completion of the scanning session, we will attempt to reschedule the session within one week of the canceled appointment. If the participant is unavailable during this time, they will be withdrawn from the study.

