#### Lost to Follow-up

A participant will be considered lost to follow-up if they fail to return for a scheduled 2nd visit and study staff are unable to contact the participant after 3 attempts.

The following actions must be taken if a participant fails to return for a 2nd session:

- The study staff will attempt to contact the participant, ascertain if the participant wishes to and/or should continue in the study, and as needed, reschedule the missed visit.
- Before a participant is deemed lost to follow-up, the study staff will make every effort to regain contact
  with the participant (where possible, 3 telephone calls, 3 text messages, or, if necessary, an email or
  certified letter to the participant's last known mailing address or local equivalent methods). These
  contact attempts will be documented in the participant's research record or study file.
- If there is any concern about the safety of a participant lost to follow-up (e.g., due to previously recorded suicidal ideation) and study staff are unable to reach the individual, then confidentiality may be broken and the COPES [contact]) may be called to help ensure safety of the participant.
- Should the participant continue to be unreachable, he or she will be considered to have withdrawn from the study with a primary reason of lost to follow-up.

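### Exclusion 8 counts medication stability back from enrolment, so an antidepressant, antipsychotic or mood-stabilizer change between Visit 1 and the scan meets no specific rule and no scheduled check

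*Protocol*

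**What the plan says.** Protocol, Section D, exclusion 8: "Change in the dose or prescription of a medication within the 6 weeks before enrolling in the study that could affect brain functioning". The examples it gives are anxiolytics, antipsychotics, antidepressants and mood stabilizers.

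The protocol does not define enrolment, but it places it in the consent process. Under Participant/Representative Comprehension: "If a participant is unable to demonstrate adequate understanding of the protocol, they will not be enrolled in the study". Consent belongs to the first visit. Under Self-Report Measures: "After the informed consent document is signed during Visit 1".

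All brain data (resting state, TReAT, diffusion) come from the second visit. MRI Scanning Visit: "Participants will be scheduled for Visit 2 one to seven days after Visit 1 is complete". After a system failure, Participant Discontinuation and Withdrawal says "we will attempt to reschedule the session within one week of the canceled appointment", and a participant who is unavailable in that time is withdrawn. The general withdrawal rule is "Participants will be withdrawn if they revoke consent or if the investigator determines that continued participation is not in their best interest". It does not name a medication change.

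Exclusion 4, in contrast, is tied to the scan day as well: "based on positive UTOX or breathalyzer test at screening or study session", with cannabis use also timed to the session.

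**The concern.** Exclusion 8 concerns drugs that may act on the brain, so its evident purpose is to keep recent changes out of the imaging measures. The window nevertheless closes before those measures are taken. A scan that follows a treatment change by a few days would count as compliant, and nothing scheduled would bring the change to light.

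The protocol already accepts that the interval matters. The version 2 rationale for rating MADRS and YMRS on the scan day is that clinical state can shift between the visits. Medication did not get the same treatment.

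The bipolar group is currently depressed or mixed with at least moderate symptoms, while controls have no current or past psychiatric disorder. Changes in the gap would therefore be expected mainly in one group. They could be read as part of the bipolar-control difference in decoded-state irregularity (second part of Hypothesis 1) and in metastability and fractal scaling (Hypothesis 2).

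**Working it through.** **1. Dates.** Let day 0 be Visit 1 and enrolment, s the scan day and c the day of a medication change. The time from change to scan is s − c.

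- As scheduled, s = 1 to 7. A change on day 1 precedes the scan by 0 to 6 days.
- After a system failure on day 7 and a reschedule within 7 days, s = 7 + 7 = 14. A change on day 1 precedes the scan by up to 13 days.
- A change 41 days before enrolment precedes the scan by 41 + 1 = 42 to 41 + 7 = 48 days and is excluded by the 42-day rule. The change on day 1, much nearer the scan, is not.

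The stretch before the scan that exclusion 8 does not cover is thus 1 to 7 days as scheduled and up to about 14 after a reschedule. Counted back from Visit 2, it is 0 days.

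**2. What other rules catch in the gap.**

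| Rule | What it reaches | Antidepressant, antipsychotic or mood-stabilizer change? |
|---|---|---|
| Exclusions 3 and 4, scan-day breath and urine tests | Alcohol and the listed drugs of abuse, including benzodiazepines and barbiturates | No |
| Exclusion 9 | Drugs affecting the hemodynamic response | Not as a class, and not triggered by a change |
| Exclusion 2 | Medical conditions that, in the investigator's opinion, could confound assessments | Not named |
| Withdrawal rule | Revoked consent, best interest, non-compliance, motion | Not named |
| Table 1 and pre-scan checks, Visit 2 | MRI safety, pregnancy, alcohol and drugs, mood and state scales | No medication question listed |

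Three of the four classes that exclusion 8 names are left without a specific rule.

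**3. The plan's own figure.** Rationale for Sampling Plan: 32 per group, 80% power, d = 0.71. Alpha and sidedness are not stated, so two-sided 0.05 is assumed. Normal approximation: n = 2(1.960 + 0.842)² / 0.71² = 15.70 / 0.5041 = 31.1, rounded up to 32. The two-sample t-test needs n = 32.1 and gives 79.8% power at 32. The stated figure is reproduced.

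**4. Power if affected bipolar scans are set aside.** The documents give no rate of change, so k is an assumed range. Controls stay at 32.

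| k of 32 set aside | Power at d = 0.71 |
|---|---|
| 0 | 79.8% |
| 1 | 79.2% |
| 3 | 77.8% |
| 6 | 75.3% |

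**5. Bias if they are kept unnoticed.** If a change moves the measure by δ SD in k participants, the bipolar mean moves by kδ/32. Per 1 SD of δ this is 1/32 = 0.03, 3/32 = 0.09 or 6/32 = 0.19 SD, against the planned 0.71. Neither δ nor its sign is known from the documents.

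**6. Plausibility of k.** If k/32 were the share changing in one week, a constant rate would imply 1 − (1 − k/32)⁶ over six weeks: 17% for k = 1, 45% for k = 3 and 71% for k = 6. Participants have just been selected for six weeks without change, so the upper end is best read as an outer bound.

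**The case against.** Eligibility criteria are normally anchored at enrolment. The text of exclusion 8 says just that, and no other sentence contradicts it. A gap of 1 to 7 days against a 42-day window is short. Stable psychotropic treatment is allowed in the bipolar group, so medication differs between the groups in any case. This stands and keeps the point small. It does not remove it: a shown or unshown analysis plan can adjust for recorded medication, but not for changes that no visit is scheduled to record.

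A reader might infer more than the document supports:

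- **That any psychotropic change in the gap breaks no rule.** Exclusions 3, 4 and 9 reach some drugs, and the investigator has general discretion.
- **That Table 1 proves no check is made.** It lists no medication review at Visit 1 either, although exclusion 8 must be checked by then, so it is not a full list of eligibility checks. The stronger evidence is that neither the rule nor the pre-scan text extends to the scan.
- **That the interval is unlimited after a missed visit.** Lost to Follow-up says only "as needed, reschedule the missed visit". It gives no limit, but it does not suspend the 1-to-7-day window.
- **That all three hypotheses are exposed.** Hypothesis 3 concerns amplification in bipolar participants and states no comparison with controls. The first part of Hypothesis 1 concerns classifier accuracy.
- **That a definite number of scans is affected.** The document supplies no rate.

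**Conclusion.** The point holds as a small, inexpensive improvement to the design, not as a contradiction in the protocol. Exclusion 8 leaves 1 to 7 days before the scan uncovered, and up to about 14 after a reschedule. In that time an antidepressant, antipsychotic or mood-stabilizer change meets no specific rule. The risk is undetected confounding, mainly on the bipolar side, in the second part of Hypothesis 1 and in Hypothesis 2. Loss of power is minor: at most 4.5 percentage points (79.8% to 75.3%) even at the outer bound of 6 scans.

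This rests on reading enrolment as part of the consent process at Visit 1, on a two-sided 5% test, and on an assumed count of affected scans. The true frequency is unknown and probably low.

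**What to change.** Count the exclusion 8 window back from the MRI visit (Visit 2), as exclusion 4 is already tied to the study session. Add one medication-change question to the Visit 2 pre-scan checks, asked again if the scan is rescheduled.

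State what follows from a reported change: the participant does not meet scan eligibility and is replaced, or is re-screened as a new entry with Visit 1 repeated. Simply holding the scan until 42 days have passed would not fit the 1-to-7-day interval between visits. At minimum, flag the scan and run a sensitivity analysis that excludes it. Say expressly that the rule governs scan eligibility and use of data only, and must not influence a participant's treatment.

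The cost is one line of protocol wording, one question on scan day and an occasional replaced bipolar participant. The sample size of 32 per group does not change.
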